### 3.9. Concomitant Medications

#### 3.9.1. P(r)EP

##### 3.9.1.1. Dried Blood Spots

The use of oral FTC/TDF as P(r)EP will be tabulated by vaccine regimen.

The prevalence of oral FTC/TDF use will be reported both as any *detectable use* and as *effective use*. More specifically, estimated percentages of persons with detectable FTC/TDF use and effective FTC/TDF use will be reported (See Table 2).

*Inferred effective use* will be measured as follow. The lower quartile of simulated TFV-DP levels in DBS at 4 doses per week is 719 fmol/punch (Castillo-Mancilla *et al.*, 2013) and 700 fmol/punch will be used as the cut-off to define effective PrEP use based on the lower quartile cited above.

An example of PrEP use report statistics is shown in [Table 3](#).

**Table 3: Detectable and Effective PrEP/PEP Use, Based on Assayed Dried Blood Spots (DBS)**

	Regimen
Time	
Number of specimens collected (assayed)	xxx (xxx)
Proportion with detectable TFV-DP level*100% (95% CI)	xx.x% (xx.x%, xx.x%)
Mean TFV-DP level (95% CI)	xx.x% (xx.x%, xx.x%)
Min-Max	xx.x%- xx.x%
Proportion >700 fmol/punch TFV-DP level*100% (95% CI)	xx.x% (xx.x%, xx.x%)
Mean TFV-DP level (95% CI)	xx.x% (xx.x%, xx.x%)
Min-Max	xx.x%-xx.x%

In addition to TDF, the DSMB might also start monitoring the use of tenofovir alafenamide (TAF) or any other antiretrovirals used as PrEP, when deemed relevant for the trial. TAF is the prodrug of TDF, and requires lower doses to attain the same exposure. Similar outputs as for TDF will be produced for the TAF assessment.

##### 3.9.1.2. Participant Reported P(r)EP Use

Additional to the DBS data on PrEP use, participant-reported data on PrEP use (through the PrEP Questionnaire and reporting in the concomitant medication) will be summarized descriptively. These will provide information on reported PrEP or PEP use, dosing, average pill count per week, and the mode of obtaining PrEP.

### 3.9.2. Other Concomitant Medications

The analysis of concomitant therapies will be done using the WHO drug coded terms.

There will be special attention to any systemic use of analgesics/antipyretics, started during 8 days following each vaccination (00:00 of day of vaccination + 7 days). Following CMCLASCD (ATC/DD codes) will be used for this: N02A (OPIOIDS) and N02B (OTHER ANALGESICS AND ANTIPYRETICS), M01A (ANTIINFLAMMATORY AND ANTIRHEUMATIC PRODUCTS, NON-STEROIDS) and M01B (ANTIINFLAMMATORY/ANTIRHEUMATIC AGENTS IN COMBINATION). The classes will be added in a footnote in all related tables and listings.

Based on their start and stop date, concomitant therapies will be reported in each applicable phase. If a concomitant therapy record misses components of its start and/or stop dates (day and/or month and/or year):

- In case of partial start or stop dates, the concomitant therapy records will be allocated to periods using the available partial information, without imputations. If, for example, only month and year are available, these will be compared to the month and the year of the periods, and the concomitant therapy record will be allocated to the period(s) where these date parts match. This rule may lead to assignment to multiple periods.
- In case of a completely missing start date, the concomitant therapy will be considered as having started before the trial.
- In case of a completely missing end date, the concomitant therapy will be considered as ongoing at the end of the trial.

## 4. SAFETY

The safety and tolerability endpoints are:

- Unsolicited AEs during the 28 days following each vaccination
- Solicited local and systemic AEs (reactogenicity), collected daily from the day of vaccination for 7 days post-vaccination (day of vaccination and the subsequent 7 days). The investigator assessment of the solicited AEs is used in the safety analysis.
- Serious Adverse Events (SAEs) and Medically Attended Adverse Events (MAAEs) during the entire course of the study.

The safety and tolerability analysis will be performed on the FAS set. Specifically, the analysis for solicited adverse events will be done on those participants in the FAS set for whom reactogenicity assessments are available in the database (either via on-site assessments or via the diary pages of the CRF).

A ‘post any dose’ period (= regimen phase in section 2.1.1) will be added, that summarizes the safety after all administered doses of the vaccine. Each participant is counted only once. Whenever a participant has the same event after more than one dose, it will be counted only once (and in case of showing attributes, the worst corresponding attribute will be shown) in the post-any dose period. The denominator will be the number of participants that received the considered dose.

### 4.1. Analysis of Adverse Events

Number and percentage of participants with at least one particular AE (unsolicited/solicited) will be tabulated. Unsolicited AEs will be summarized by System Organ Class and Preferred Term. Solicited AEs will be summarized by class (administration site, systemic) and preferred term.

For solicited AEs following tables will be provided: summary, by worst severity grade, grade 3 or above, related (systemic only), time to onset (in days) and duration (in days) for most frequent events and body temperature. Note: Duration is defined as number of days from the start of the event until resolution of the event. The time to first onset is defined as (date of first onset – reference date + 1). The reference date is the start date of the vaccination period.

For unsolicited AEs following tables will be provided: summary table (including SAE, fatal outcome, AESI and discontinuation), all events, most frequent, grade 3 or above, permanent stop of vaccine, related, SAE and AESI.

Listings and/or participant narratives will be provided as appropriate, for those participants who die, discontinue study vaccinations due to an AE, or experience a severe or serious AE.

### 4.2. Phase allocation of Adverse Events

Solicited events are always allocated to the respective Post Dose period.

**Step 1: Allocation of events to the periods:**

Adverse events in the SDTM database are allocated to periods based on their start date/time. If the start date/time of an event falls between (or on) the start and stop date/time of a period, the AE is attributed to that period (treatment-emergent principle).

- In case of partial start or stop dates (i.e. time and/or day and/or month and/or year missing), the events are allocated to the periods using the available partial information on start and end date; no imputation will be done. If, for instance, the AE start date only month and year are available, these data are compared to the month and year information of the periods. This rule may lead to multiplication of the event as a consequence of its assignment to multiple periods.
- In case of a completely missing end date, the date is imputed by the cut-off date of the analysis for participants still ongoing in the study, and by the end date of the last period for participants who discontinued or completed the trial. In case of a completely missing start date, the event is allocated to the first active treatment phase (post dose 1 period), except if the end date of the AE falls before the start of the first active treatment phase (post dose 1 period).

**Step 2: Combination of events:**

Overlapping/consecutive events are defined as events of the same participant with the same preferred term which have at least 1 day overlap or for which the start date of an event is 1 day after the end date of the preceding event. Overlapping/consecutive events may be combined into one AE or not, according to the following rules:

- 1) If overlapping/consecutive events start in one of the following periods - Screening or post dose extension (i.e. non-active periods) - followed by an AE in - post-dose period (active period) - they are allocated to their respective periods and are considered as separate events.
- 2) In case overlapping/consecutive events start within a single period, they are considered as one and the same AE. The individual events which contribute to this AE are retained as individual records in the ADaM database but are assigned the same onset, period, and total duration. All related attributes to the AE/phase/period should also be consistent with the new event.
- 3) In case overlapping/consecutive events start in both an active period followed by a nonactive period, they are allocated to the active period only and are considered as one and the same AE. The individual events which contribute to this AE are retained as individual records in the ADaM database but are assigned the same onset, treatment period, and total duration. All related attributes to the AE/phase/period should also be consistent with the new event.
- 4) In case an active period is followed by another active period, and the overlapping/consecutive events start in both periods, they are allocated to their respective period and are considered as separate AEs. The same rule applies for 2 non-active periods.

**Remarks:**

1. Events can only be combined into one and the same AE if their start and stop dates are known.
2. In case the completely missing end date is imputed (for period allocation), this date is also considered as a complete date.
3. Time is not considered when determining overlap of events.

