**4.3. Missing Data**

Missing data will not be imputed. Participants who do not report an event will be considered as participants without an event. An AE with a missing severity or relationship will be considered as an AE reported, but will be considered as not reported for the severity or relationship. For example, an AE with missing severity will be considered as an AE reported for the analysis of any grade, but will be considered as not reported for the analysis of grade 3 or above.

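### SAP 4.2 Remark 2 treats an imputed AE end date as known, so a later same-term episode in follow-up can be merged into an earlier 28-day post-dose period

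*SAP*

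**What the plan says.** The rules are in SAP Section 4.2.

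- **Allocation (Step 1).** "Adverse events in the SDTM database are allocated to periods based on their start date/time".
- **Missing end date (Step 1).** "In case of a completely missing end date, the date is imputed by the cut-off date of the analysis for participants still ongoing". Those who have left or finished get the close of their final period instead. Partial dates are used as they stand, without imputation.
- **Overlap (Step 2).** Events overlap if they belong to one participant and have the "same preferred term which have at least 1 day overlap". An event that starts the day after the previous one ended is treated the same way.
- **Rule 3 (Step 2).** This covers a pair whose first event begins in an active period and whose second begins in a non-active one. The SAP's instruction is that "they are allocated to the active period only and are considered as one and the same AE". The contributing records stay in the ADaM data set but receive a common onset, period and total duration, and their attributes are aligned with the combined event.
- **Rules 1, 2 and 4 (Step 2).** Rule 2 combines events that start in the same period. Rules 1 and 4 keep separate the pairs that run from non-active to active, active to active, and non-active to non-active.
- **Remarks.** Remark 1 allows combination only when start and stop dates are known. Remark 2 adds: "In case the completely missing end date is imputed (for period allocation), this date is also considered as a complete date".

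SAP Section 4.3 states for the safety data: "Missing data will not be imputed". SAP Section 2.1.1 classes the post-dose periods as active, and screening and the follow-up phases as non-active. SAP Section 2.1 says that all safety results are presented by phase.

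**The concern.** Remark 1 is a sensible safeguard: two records should be called one event only when their dates show that they overlap. Remark 2 removes the safeguard where least is known. An AE with no end date at all is stretched to the end of follow-up, so it overlaps every later record of that term in that participant. An AE with a partial end date, about which more is known, is not imputed and so fails Remark 1.

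The split between post-dose and follow-up is what the phase tables are meant to show. A late episode that is serious, of higher grade or judged related could be displayed within 28 days of a dose when it began many months later, and the follow-up table for that term would omit it.

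Repeat events of one term are plausible here. Under protocol Section 9.4, a sexually transmitted infection found at a study visit and then treated counts as a medically-attended AE, and such AEs are collected throughout the study. Protocol Sections 9.1.4 and 9.1.5 schedule syphilis, chlamydia and gonorrhea tests at Visits 4, 7, 10, 12 and 14.

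**Working it through.** The plan gives no figure to reproduce. The check is to apply the rules to the planned periods.

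**Inputs.** Doses are on Days 1, 84, 168 and 364, and Month 30 is Day 910 (protocol Section 9.1.2, nominal days). Each post-dose period runs from the dose day to the dose day + 28, followed by a follow-up phase until the next dose (SAP Table 1). The table's stop rules for Post-Dose 3 and 4 refer to the second vaccination; I read them as the respective dose.

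**Which pairs move.** Screening, four post-dose periods and four follow-up phases make 9 intervals, so there are 9 × 10 / 2 = 45 ordered pairs of start intervals, same-interval pairs included.
- Rule 3 (active, then non-active): 4 + 3 + 2 + 1 = 10 pairs if any later follow-up phase counts, or 4 if only the directly following phase counts.
- Rule 2 (same interval): 9 pairs, merged without being moved.
- Rule 1 (non-active, then active): 4 + 3 + 2 + 1 = 10 pairs, kept separate.
- Rule 4: 6 active-active + 10 non-active pairs = 16, kept separate.

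On the broad reading of rule 3 the total is 10 + 9 + 10 + 16 = 45. On the narrow reading, 10 − 4 = 6 pairs fall under no stated rule.

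**Exposed days.** Follow-Up 1 is Days 30–83 (54 days), Follow-Up 2 is Days 113–167 (55), Follow-Up 3 is Days 197–363 (167) and Follow-Up 4 is Days 393–910 (518). For an AE without an end date that starts in a given post-dose period, a new same-term episode is moved back if it starts on one of these days:

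| AE starts in | Directly following phase only | Any later follow-up phase | All later days to Day 910 | Share, broad reading |
|---|---|---|---|---|
| Post-Dose 1 | 54 | 54 + 55 + 167 + 518 = 794 | 910 − 29 = 881 | 90.1% |
| Post-Dose 2 | 55 | 55 + 167 + 518 = 740 | 910 − 112 = 798 | 92.7% |
| Post-Dose 3 | 167 | 167 + 518 = 685 | 910 − 196 = 714 | 95.9% |
| Post-Dose 4 | 518 | 518 | 910 − 392 = 518 | 100% |

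Post-Dose 4 is the clean case because no dose follows it, so both readings agree. SAP Table 1 puts Dose 4 on Day 337 instead. Follow-Up 4 is then Days 366–910, or 545 days, and the share is still 100%.

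**Example.** Assume that an infection is recorded with onset on Day 364 after the dose and has no end date. A new episode of the same term starts at Month 18, 24 or 30 (Days 546, 728 and 910). It is placed in Post-Dose 4, which is 182, 364 or 546 days before it began.

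**Is the imputed date needed?** Not for an event with a known start, because Step 1 allocates by start. End-date information matters for allocation only when the start is partial or wholly missing. For all other events, the imputed date affects only the overlap test and the duration.

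**The case against.** The case for leaving the rule alone has several sound parts.

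- **No false post-dose event.** A reader might infer that the rule puts an event into the post-dose period that does not belong there. Rule 3 applies only if the first AE already started there, and SAP Sections 4 and 4.1 count participants with at least one event. The any-grade count of the term does not rise; only attributes can change.
- **No lost record.** A reader might infer that the later medically-attended AE vanishes. Step 2 keeps the individual records in ADaM. What is lost is its separate place in the follow-up-phase tables.
- **No distorted duration table.** A reader might infer that reported durations are inflated. SAP Section 4.1 lists duration only for solicited AEs, and Section 4.2 always keeps those in their own post-dose period. The unsolicited tables listed there contain no duration.
- **A blank end date may mean ongoing.** Protocol Sections 9.4 and 12.3.1 follow AEs to resolution or clinical stability. For an AE that is truly ongoing, the overlap is real and merging is right. The SAP does not say how ongoing and unknown end dates are told apart; the eCRF guidelines may.
- **Section 4.3 is a weak contradiction.** Its examples concern unreported events and missing severity or relationship, while Section 4.2 is the specific rule for dates. A cross-reference would settle it.
- **The scope is narrow.** Solicited events are unaffected. Outside the 28-day windows, mainly serious AEs, medically-attended AEs, AEs leading to discontinuation and (up to 6 months after the last dose) AEs of special interest are collected. Safety is descriptive, with no formal testing (protocol Section 11.6).

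All of this stands, and it limits the point without removing it. None of it prevents a late episode's grade, seriousness or relatedness from being shown as post-dose when the earlier end date is simply unknown.

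**Conclusion.** The point holds as a minor correction to descriptive safety tables. Remark 2 lets an imputed end date override Remark 1. An unsolicited AE that starts post-dose and has no end date can then absorb a separate later episode of the same term that starts in follow-up. After Dose 4 this applies to all 518 later nominal days to Month 30, on either reading of rule 3. After Doses 1 to 3 it applies to 54, 55 and 167 days on the narrow reading, or 794, 740 and 685 on the broad one.

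These are exposure windows, not event counts. They assume nominal visit days and follow-up to Month 30, and they shorten for anyone whose follow-up ended earlier. The documents give neither the rate of missing end dates nor the rate of same-term recurrence, so the number of affected participants cannot be derived. Attributes shift only if the later episode is worse, serious or related where the first was not. The documents support no claim of extra any-grade post-dose events, deleted records or changed duration tables.

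**What to change.** Limit Remark 2 to AEs explicitly recorded as ongoing. State that, when the end date is unknown, an imputed date is not used to combine events or to compute duration; Remark 1 then applies as written. In the same edit, say whether rule 3 covers only the directly following follow-up phase or any later one, and cross-refer Section 4.3 to the date rules in Section 4.2.

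The SAP's amendment history records study-level unblinding on 18 January 2023. The change should therefore be documented as made after unblinding. Alternatively, keep the rule and add a sensitivity table of the unsolicited AE summaries by phase without such merging.

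The core change costs one sentence in Section 4.2 and one step in the AE combination program. The downside is a few more separate AE records.

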**4.3. Missing Data**

Missing data will not be imputed. Participants who do not report an event will be considered as participants without an event. An AE with a missing severity or relationship will be considered as an AE reported, but will be considered as not reported for the severity or relationship. For example, an AE with missing severity will be considered as an AE reported for the analysis of any grade, but will be considered as not reported for the analysis of grade 3 or above.

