After each vaccination, participants will remain under observation at the study site for at least 30 minutes for presence of any acute reactions. In addition, participants will record solicited signs and symptoms in a diary for 7 days post-vaccination. These participants will be provided with a diary and instructions on how to complete the diary (Section 9.1.1). The study staff will transcribe the information provided by the participant into the relevant sections of the CRF. After review and verbal discussion of the initial paper diary entries with the participant, the investigator will complete his/her own assessment in the relevant sections of the CRF. Once a solicited sign or symptom from a diary is considered to be of severity Grade 1 or above, it will be recorded as a solicited adverse event. For grading of solicited adverse events, see Section 12.1.3. For solicited adverse events, the investigators will document them in the clinic note, followed by entry into the CRF.

Solicited Administration Site Adverse Events

Participants will be asked to note in the diary occurrences of pain/tenderness, erythema and swelling at the study vaccine administration site daily for 7 days post-vaccination (day of vaccination and the subsequent 7 days). The extent (largest diameter) of any erythema, and swelling should be measured (using the ruler supplied) and recorded daily. ^{12,25}

Solicited Systemic Adverse Events

Participants will be instructed on how to record daily temperature using a thermometer provided for home use. Participants should record the temperature in the diary in the evening of the day of vaccination, and then daily for the next 7 days approximately at the same time each day. If more than one measurement is made on any given day, the highest temperature of that day will be used in the CRF.

Fever is defined as endogenous elevation of body temperature $\geq 38^{\circ}\text{C}$, as recorded in at least one measurement.²⁷

Participants will also be instructed on how to note daily in the diary signs and symptoms for 7 days post-vaccination (day of vaccination and the subsequent 7 days) of the following events: fatigue, headache, nausea, myalgia, chills, arthralgia, and vomiting.

Clinical Laboratory Tests

No blood samples for safety laboratory testing will be collected. However, clinical laboratory assessments to be performed are as follows:

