- During COVID-19-related pauses, study vaccine administration is put on hold. At the next possible on-site visit, the study vaccine may be administered. Vaccination outside of the window can be assessed on a case-by-case basis following approval and recommendations from the safety review team and will be documented as 'COVID-19-related'.

Other Study Visits and Assessments

- When site visits are not possible, sites should collect the assessments via remote visits or via home visits (if possible and if the participant allows and provides consent to it). For participants having received one or more vaccinations, post-vaccination visits can be conducted remotely with the main objective to collect safety and reactogenicity data, if possible. The actual visit date and the type of visit (ie, remote or home visit) should be captured in the eCRF according to the eCRF completion guidelines.
- Procedures that can't be performed in case of remote visits (eg, blood/urine sampling, swabbing), including missed assessments related to efficacy endpoints (in-study HIV testing and sampling for immunogenicity testing), should be documented as protocol deviations and labelled as "missed due to COVID-19". The protocol deviations need to be captured in the source document.
- Reactogenicity assessment should be discussed during the remote visits. Diary reconciliation by the investigator will be done at the next possible on-site visit or at a home visit if possible and agreed by the participant. At the end of the study, all diaries should be on site for final reconciliation and filed in participants' folders.

Sample Management

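### Read literally, the SAP keeps a vaccinee with no reactogenicity data for a dose in that dose's denominator as reaction-free, which lowers the per-dose solicited-event rates

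*SAP*

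**What the plan says.** Three SAP rules bear on the solicited-event tables.

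- **Who is analysed (SAP 4).** "the analysis for solicited adverse events will be done on those participants in the FAS set for whom reactogenicity assessments are available in the database", where available means "either via on-site assessments or via the diary pages of the CRF". The condition is on the participant. No dose is mentioned.
- **Denominator (SAP 4, at the end of the paragraph on the post-any-dose period).** "The denominator will be the number of participants that received the considered dose".
- **Missing data (SAP 4.3).** "Missing data will not be imputed", followed by "Participants who do not report an event will be considered as participants without an event". The section covers adverse events in general and makes no exception for solicited ones.

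Protocol 11.6.1 counts each solicited event once per participant, at maximum severity, for each vaccination dose, so the unit of reporting is the dose. Protocol 9.4 collects these events in a diary on the day of vaccination and the following 7 days. Reactogenicity is part of the first secondary objective (Protocol 2.1, SAP 1.1). Protocol 11.6 plans no formal testing of safety data.

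**The concern.** For unsolicited events, treating silence as absence is an ordinary convention. Solicited events differ: they are asked about daily over a fixed window, so a dose with no entries is a dose that was not assessed, not a dose without reactions.

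The restriction in SAP 4 handles this for a participant who has no reactogenicity data at all. It does not clearly handle the intermittent case. Take a participant with diary data after doses 1 and 2 and none after dose 3. That participant has assessments available and so is in the analysis set, received dose 3 and so is in its denominator, and reported nothing after dose 3 and so counts as without an event under 4.3.

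Because safety is not tested, the percentages themselves are the reactogenicity result. Equal loss of data in both arms shrinks every rate and the vaccine-placebo difference by the same factor. Unequal loss between doses or arms would distort those comparisons.

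**Working it through.** **The plan's own figure.** The documents state no expected solicited-event rate and no missing-diary share. The nearest safety figure, in Protocol 11.3 and SAP 1.4, is an 85% chance of seeing at least one event of true rate 1/1,000 among 1,900 vaccinees. It reproduces: 1 - 0.999^1900 = 85.06%. It says nothing about the denominators at issue.

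**Inputs, all assumed for illustration.** p = true proportion with the solicited event after a dose. m = share of recipients of that dose, within the solicited-event analysis set, who have no reactogenicity data for it.

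**Literal rule.** Only the observed share (1-m) can contribute events, but all recipients are in the denominator. If missingness is unrelated to reactions, the expected reported rate is p(1-m) and the shortfall is p x m.

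| p | m | Reported | Shortfall (points) |
|---|---|---|---|
| 60% | 2% | 58.8% | 1.2 |
| 60% | 5% | 57.0% | 3.0 |
| 60% | 10% | 54.0% | 6.0 |
| 30% | 2% | 29.4% | 0.6 |
| 80% | 10% | 72.0% | 8.0 |

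In counts, with 1,900 recipients and m = 10%: 190 have no data, the other 1,710 yield 0.60 x 1,710 = 1,026 with the event, and 1,026/1,900 = 54.0%. Dividing by those with data gives 1,026/1,710 = 60.0%.

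**Between arms.** With assumed true rates of 60% (vaccine) and 25% (placebo) and the same m in each arm, the true difference is 35 points. At m = 5% it is 57.0 - 23.75 = 33.25. At m = 10% it is 54.0 - 22.5 = 31.5.

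**If missingness is related to reactions.** Let p_obs be the rate among recipients with data and q the rate among those without. The true rate is p_obs(1-m) + qm. The literal rule reports p_obs(1-m), which is too low by qm. A denominator of recipients with data reports p_obs, which is off by m(p_obs - q). With p_obs = 60% and m = 10%:

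| q | Error, literal rule | Error, recipients with data |
|---|---|---|
| 60% | -6.0 points | 0 |
| 30% | -3.0 points | +3.0 points |
| 0% | 0 | +6.0 points |

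The literal rule is exact only if nobody with missing data reacted. The denominator with data is closer to the truth whenever q exceeds half of p_obs.

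**The case against.** The strongest reply is that the restriction in SAP 4 was meant dose by dose. Solicited events are tabulated per dose, the denominator sentence closes the paragraph on the pooled post-any-dose period, and it may operate within the set already restricted to available data. On that reading there is no bias. This stands as a possible reading, but the SAP does not state it. Mock tables and programming details are in the Data Presentation Specifications (SAP 1), which are not among the documents and may settle the matter.

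Three stronger readings are tempting, and the documents do not support them.

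- **That everyone without a diary is counted as reaction-free.** A participant with no reactogenicity assessments at all is outside the analysis set.
- **That the post-dose observation satisfies the restriction for every vaccinee.** Protocol 9.4 says: "After each vaccination, participants will remain under observation at the study site for at least 30 minutes for presence of any acute reactions". It then describes the diary as additional. Nothing equates that observation with a reactogenicity assessment. The on-site assessment in SAP 4 may mean the investigator's own assessment of solicited events, which SAP 4 uses for the analysis.
- **That COVID-19 lowers diary return, especially at doses 3 and 4.** Protocol 18 says: "Diary reconciliation by the investigator will be done at the next possible on-site visit or at a home visit if possible". That concerns timing, not loss. The same appendix puts vaccination on hold during pauses, has reactogenicity discussed at remote visits, and expects all diaries on site by study end.

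It is also fair that an unreturned diary need not mean an unobserved week. Protocol 9.1.5 plans a contact after every dose (Visits 2a, 3a, 4a and 7a) and, in general, clinician review of reactions greater than mild. This lowers m where the investigator records an assessment. It does not change how the remaining doses are counted.

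**Conclusion.** The point holds in a limited form. Applied literally, SAP 4 and 4.3 together score a participant who has data for some doses but not for the one tabulated as having had no reaction to it. The expected loss is p x m points. Over assumed ranges of p = 30% to 80% and m = 2% to 10%, that is 0.6 to 8.0 points, and at p = 60% with m = 5% to 10% it is 3 to 6 points. These figures rest on assumed rates, on missingness unrelated to reactions, and on the literal reading. Under a dose-by-dose reading the loss is zero.

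The effect is confined to descriptive secondary safety tables. The primary efficacy analysis is untouched. A change is still warranted, because the rules as written can put a known downward error into a secondary result, and two programmers could derive different percentages from the same text.

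**What to change.** In SAP 4 and 4.3:

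1. Define the denominator of each per-dose solicited-event table as participants who received that dose and have reactogenicity data for it (diary or investigator assessment).
2. For the post-any-dose table, require such data for at least one dose.
3. Limit the rule that no report means no event to unsolicited events, and to solicited events within doses that have reactogenicity data.
4. Tabulate the number of administered doses without reactogenicity data, by dose and arm.

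The cost is SAP wording, one derived flag per dose and one small table, with no new data collection. If a per-dose denominator was always intended, this only writes it down. Reported reactogenicity may come out slightly higher, and could be overstated if people with reactions return diaries more often. The table in item 4 would help readers judge that. The SAP's amendment history dates its last two versions after study-level unblinding, so the change should be recorded as made after unblinding.
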